10.3.1 Analysis Population

Intent-to-Treat Population (ITT): The ITT population will include all subjects who are enrolled in the study. The ITT population will be the primary population for evaluating efficacy and subject characteristics.

As-Treated Population (AT) The AT population will include all subjects who receive at least 1 course of study therapy. The AT population will be the primary population for evaluating safety. If a patient does not receive any vaccine and poly-ICLC (strata A and B) in combination with nivolumab (stratum C), they will be replaced for evaluation of safety.

10.3.2 Analysis of Primary Endpoints

- Safety of K27M/TT vaccine and poly-ICLC in combination with nivolumab (stratum C only) will be assessed by monitoring for adverse events, scheduled laboratory assessments, vital sign measurements, and physical examinations for subjects who receive at least one course of the study therapy. The severity of toxicities will be graded according to the NCI CTCAE v5.0. Adverse events and will be summarized by maximum intensity and relationship to study drug(s).
- Safety will be assessed every 3 weeks for the first 24 weeks and then every 6 weeks. Descriptive statistics will be utilized to display the data on toxicity seen.
- OS12 in HLA-A02:01⁺ children with H3.3K27M positive DIPG (Stratum A) will be the clinical efficacy primary endpoint. Any subject enrolled (ITT) will be considered evaluable for clinical efficacy. Patients lost to follow-up before 12 months will be considered events and the OS probability at 12 months (OS12) will be estimated from the Kaplan-Meier method. Two-sided 95% CI will be computed based on the Greenwood's formula.

10.3.3 Analysis of Secondary Endpoints

CTL response based on ELISPOT: A subject will be considered to have responded, if at any of postvaccine time point against H3.3K27M antigen, the number of spots is double that at baseline, and there are at least 10 spots/20,000 cells, and if the number of the post-vaccine spots is at least three times the standard-deviation of the pre-vaccine value. This definition provides some protection against false positive response. We will correlate response with OS data. We will plot the time course of the magnitude of response and model it using a mixed-effects model approach.

10.3.4 Other Analyses/Assessments

The other exploratory aims associated with this study will be descriptive and will be limited to frequency tables and summary statistics.

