	The Study Chair is responsible for the overall conduct of the study and for monitoring its safety and progress at all participating sites.		
Efficacy Assessments	Overall Survival at 12 months for stratum A and stratum C.		
Unique Aspects of this Study	This is the first study to evaluate the safety and efficacy of specific synthetic peptide for the H3.3.K27M epitope alone and in combination with PD-1 inhibition with nivolumab in HLA-A2 (02:01) ⁺ children with newly diagnosed H3.3K27M		

	positive DIPG or other H3.3K27M positive midline gliomas.
--	---

Therapy Schema

XRT following diagnosis of H3.3K27M and HLA-A*02:01 positive DIPG (n=19), other H3.3K27M and HLA-A*02:01 positive gliomas, including spinal cord gliomas (n=10) and other HLA-A2 (02:01)+ children with H3.3K27M DIPG and positive midline gliomas other than DIPG, excluding spinal cord tumors (n=20).

List of Abbreviations

AE	adverse event
ALP	alkaline phosphatase
ALT	alanine aminotransferase
ANC	absolute neutrophil count
AST	aspartate aminotransferase
BUN	blood urea nitrogen
CBC	complete blood cell (count)
CR	complete response
CRC	Clinical Research Coordinator
CRF	case report form
CSF	cerebral spinal fluid
CTCAE	Common Terminology Criteria for Adverse Events
CTL	Cytotoxic T Lymphocyte
CTMS	Clinical Trial Management System
DIPG	Diffuse intrinsic pontine glioma
DLT	dose limiting toxicity
DSMC	Data and Safety Monitoring Committee
DSMP	Data and Safety Monitoring Plan
FDA	Food and Drug Administration
GAA	Glioma associated antigens
GBM	Glioblastoma multiforme
GCP	Good Clinical Practice
GMP	Good Manufacturing Practice
HDFCCC	Helen Diller Family Comprehensive Cancer Center
HGB	Hemoglobin
HGG	High grade glioma
HLA	Human leukocyte antigen
IFA	Incomplete Freund's adjuvant
IHC	immunohistochemistry
IM	intramuscular
IND	investigational new drug application
IRB	Institutional Review Board
IV	Intravenous
K27M/TT	H3.3K27M/Tetanus Toxoid vaccine

List of Abbreviations

MRI	magnetic resonance imaging
NABTC	North American Brain Tumor Consortium
NABTT	New Approaches for Brain Tumor Therapy
NCI	National Cancer Institute
ORR	overall response rate
OSR	overall survival rate
OS12	Overall survival at 12 months
PBMC	Peripheral blood mononuclear cell
PD	Progressive disease
PD-1	Programmed cell death protein 1
Poly-ICLC	Polyinosinic-Polycytidylic acid with polylysine and carboxymethylcellulose
PR	partial response
PRC	Protocol Review Committee (UCSF)
RLT	Regimen limiting toxicity

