10.1.2 Exploratory Endpoints

Stratum A:

 Induction of the H3.3K27M epitope-specific CTL response in post vaccine PBMCs in HLA-A2 (02:01)+ children with H3.3K27M positive gliomas other than DIPG
- Assessment of H3.3K27M infiltrates in subjects with evidence of progression that undergo tissue collection as part of their standard of care. Tumor tissue will be analyzed for H3.3K27M expression status and infiltration of H3.3K27M specific T cells
- To archive tumor and normal DNA from each subject at time of initial diagnosis along with serial blood draws following therapy to determine whether circulating tumor DNA (ctDNA) sequences in the subject's blood serve as biomarkers of tumor burden, response to therapy, or development of drug resistance.

Stratum B:

- Induction of the H3.3K27M epitope-specific CTL response in post vaccine PBMCs in HLA-A2 (02:01)+ children with H3.3K27M positive gliomas other than DIPG
- Assessment of H3.3K27M infiltrates in subjects with evidence of progression that undergo tissue collection as part of their standard of care. Tumor tissue will be analyzed for H3.3K27M expression status and infiltration of H3.3K27M specific T cells
- To archive tumor and normal DNA from each subject at time of initial diagnosis along with serial blood draws following therapy to determine whether circulating tumor DNA (ctDNA) sequences in the subject's blood serve as biomarkers of tumor burden, response to therapy, or development of drug resistance.

Stratum C:

- To determine the OS12 in HLA-A2 (02:01)⁺ children with H3.3K27 positive DIPGs and midline gliomas (excluding primary spinal cord tumors) that are treated with repeated administration of the H3.3K27M peptide and nivolumab.
- Induction of the H3.3K27M epitope-specific CTL response in post vaccine PBMCs in HLA-A2 (02:01)+ children with H3.3K27M positive gliomas including DIPG or other H3.3K27M positive midline gliomas, excluding primary spinal cord tumors.
- To archive tumor and normal DNA from each subject at time of initial diagnosis along with serial blood draws following therapy to determine whether circulating tumor DNA (ctDNA) sequences in the subject's blood serve as biomarkers of tumor burden, response to therapy, or development of drug resistance.
- To assess Quality of Life (QoL) and cognitive measures in HLA-A2 (02:01)⁺ children with H3.3K27M positive DIPG or other midline gliomas.

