With a null hypothesis that OS12 is 40%, a sample size of 19 patients achieves 80% power to detect a difference of 30% using a one sided exact binominal test⁴⁰. The target significance level is 5% and the actual significance level is 3.5% with this test. If 12 or more patients are alive at 12 months, the null hypothesis that OS12 is 40% will be rejected. Patients lost to follow-up before 12 months will be considered events. OS12 will be estimated from the Kaplan-Meier method. Two-sided 95% CI will be computed based on the Greenwood's formula. If the null hypothesis is truly OS12 = 30% or OS12 = 50%, a sample size of 19 patients still achieves 80% power to detect a difference of 30%, however, the number of patients needed to reject the null changes to n = 10 or n = 14, respectively.

For the secondary endpoint for stratum C, we will assess the efficacy endpoint (OS12) in 20 evaluable patients with H3.3K27M positive DIPG or other midline gliomas, excluding primary spinal cord tumors.

In comparing outcomes to other H3K27M positive midline gliomas, OS rates similar to those for Stratum A are reported, although the reference literature is sparser for this patient population^{31,32}. Thus, similar to stratum A, a sample size of 20 patients achieves 80% power to detect a difference of 30% using a one sided exact binominal test (see above)⁴⁰.

At time of data analysis, we will use the most recent published data and PNOC enrollment data in order to determine the appropriate null rate for stratum A and stratum C.

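### Stratum C OS12 is exploratory and descriptive-only under 2.2, 10.1.2 and 10.3.4, but secondary with a powered exact test in 10.2.1, and no analysis section says which applies

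*Combined protocol and SAP*

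**What the plan says.** The combined protocol and SAP deals with Stratum C OS12 in several places.

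- **Objectives and endpoints.** Section 2.2 places it among the exploratory objectives. In 10.1.2 the Stratum C exploratory list opens with an aim that begins "To determine the OS12 in HLA-A2" and covers DIPG and "midline gliomas (excluding primary spinal cord tumors) that are treated with repeated administration of the H3.3K27M peptide and nivolumab". Section 10.1 has a primary list and an exploratory list, and no secondary list.
- **Sample size (10.2.1).** Here it is secondary: "For the secondary endpoint for stratum C, we will assess the efficacy endpoint (OS12) in 20 evaluable patients". By analogy with Stratum A, "a sample size of 20 patients achieves 80% power to detect a difference of 30% using a one sided exact binominal test". The section ends by saying that the null rate for both strata will be chosen when the data are analysed.
- **Primary analyses (10.3.2).** OS12 is covered for Stratum A only. That bullet contains the rule "Patients lost to follow-up before 12 months will be considered events and the OS probability at 12 months (OS12) will be estimated", together with the Kaplan-Meier estimator and the Greenwood interval.
- **Secondary analyses (10.3.3).** Only the ELISPOT response appears. Survival enters in one sentence: "We will correlate response with OS data".
- **Remaining analyses (10.3.4).** "The other exploratory aims associated with this study will be descriptive and will be limited to frequency tables and summary statistics".
- **Synopsis, Efficacy Assessments.** "Overall Survival at 12 months for stratum A and stratum C", with no ranking and no test named.

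**The concern.** OS12 is the only clinical efficacy endpoint listed for the nivolumab combination. Section 1.3 puts forward the hypothesis that the combination works better than vaccine alone, so readers will look to this number. The plan gives it two statuses with different consequences: a hypothesis test with a stated power, or a table. In a single-arm, open study the survival outcomes are visible as they accrue. Unless the choice is fixed in advance, it can be made with the result known. The same holds for the null rate, which 10.2.1 leaves until analysis.

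**Working it through.** **1. Which analysis rule reaches Stratum C OS12?** Section 10.3.4 does not name it. It does cover whatever exploratory aims remain after 10.3.2 and 10.3.3. CTL response is on the exploratory list in 10.1.2 and is taken out by 10.3.3. Stratum C OS12 is on the same list and is taken out by neither section. Read with 10.1.2, it therefore falls under 10.3.4 and has no test. If the secondary label of 10.2.1 is preferred, 10.3.3 is where its analysis should be, and it is not there. The gap remains on both readings.

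**2. Reproduce the Stratum A design.** Inputs from 10.2.1: n = 19, null 40%, alternative 40% + 30 points = 70%, one-sided target 5%, reject at 12 or more alive. For r or more alive, with X binomial (n, p):

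P(X ≥ r) = Σ from k = r to n of C(n, k) p^k (1 − p)^(n − k)

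- Under p = 0.40: P(X ≥ 12) = 0.0352, and P(X ≥ 11) = 0.0885. The cut-off of 12 and the actual level of 3.5% reproduce.
- Under p = 0.70: P(X ≥ 12) = 0.818, in line with the stated 80%.
- The alternative cut-offs of 10 (null 30%) and 14 (null 50%) also reproduce, with power 0.814 and 0.837.

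**3. Apply the same rule to Stratum C.** Inputs: n = 20 and a 30-point difference (10.2.1); 5% one-sided target and 40% null taken over from Stratum A, as the cross-reference implies; nulls of 30% and 50% because 10.2.1 considers them.

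| Null | Alternative | Smallest cut-off with level ≤ 5% | Level | Level one count lower | Power |
|---|---|---|---|---|---|
| 30% | 60% | 10 of 20 | 4.8% | 11.3% | 87.2% |
| 40% | 70% | 13 of 20 | 2.1% | 5.65% | 77.2% |
| 50% | 80% | 15 of 20 | 2.1% | 5.8% | 80.4% |

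At the 40% null the stated 80% does not reproduce: power is 77.2%, a shortfall of 80 − 77.2 = 2.8 points. Using the Stratum A count of 12 with 20 patients would give a level of 5.65%, above target.

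**4. What the conflict does to a result.** Take 13 of 20 alive at 12 months, no losses, null 40%.

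- Under 10.2.1: p = P(X ≥ 13) = 0.021, so the null is rejected.
- Under 10.3.4: 13/20 = 65% is tabulated, and no test is made.

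For comparison, a descriptive report with an interval would read as follows. Without censoring, Greenwood's standard error is √(0.65 × 0.35 / 20) = 0.107, and 0.65 ± 1.96 × 0.107 gives about 44% to 86%.

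**5. Population and losses.** Section 10.3.1 makes ITT the primary efficacy population for the whole study, so the Stratum C denominator is settled. The losses-as-events rule, the estimator and the interval stand in the Stratum A paragraph of 10.2.1 and the Stratum A bullet of 10.3.2. The Stratum C paragraph refers back to that text when it discusses power and the test.

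**The case against.** The strongest reply is that 10.3.4 names no endpoint, and that the plan already treats an item on the exploratory list (CTL response) as secondary. On that usage, Stratum C OS12 is secondary because 10.2.1 says so, the test applies, and the defect is a labelling slip plus an omission from 10.3.3. This is a fair reading, and it means the two rules are not beyond reconciling. But nothing in the plan selects it over the other reading, and it still leaves the endpoint without a written analysis.

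The reply also has weight on importance. The only primary endpoint of Stratum C is safety (10.1.1), and no section defines what a positive Stratum C would be.

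A reader might infer more: that the handling of losses is wholly open, so that two lost children could change the verdict. Assume 12 alive, 6 dead and 2 lost, with a 40% null. Losses as events give 12/20 and p = 0.057. Dropping them gives 12/18 and p = 0.020. The documents do not support this inference. Section 10.3.1 keeps every enrolled child in the efficacy denominator, so 12/18 departs from the plan. Section 10.3.4, the only section that could lead to a bare table, allows no test on it. The reference back to Stratum A can also be read as carrying the loss rule over. What stands is narrower: no sentence states the loss rule, estimator or interval for Stratum C, so the carry-over is arguable rather than explicit.

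**Conclusion.** The plan is inconsistent on whether Stratum C OS12 is tested. Under 2.2, 10.1.2 and 10.3.4 it is described; under 10.2.1 it is tested; 10.3.2 and 10.3.3 do not decide. At 13 of 20 alive and a 40% null, this is the difference between a rejection at p = 0.021 and no formal conclusion.

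The 10.2.1 test could not be carried over unchanged in any case. It has no Stratum C cut-off, and its null is set after the data. Over the nulls of 30% to 50% that 10.2.1 considers, the cut-off runs from 10 to 15 of 20. Its stated 80% power is 77.2% at the 40% null.

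These figures assume exactly 20 children in the analysis, a one-sided 5% level as in Stratum A, and no losses. The point should be corrected, but it does not touch the Stratum C primary analysis of safety or the Stratum A efficacy test. It does not show that the population is undefined or that losses may be dropped.

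**What to change.** Give Stratum C OS12 one label in 2.2, 10.1.2, 10.2.1 and 10.3, and then take one of two routes.

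- **(a) Keep the test.** Name the endpoint in 10.3.3 as secondary and exclude it from 10.3.4. State that it is analysed as in Stratum A: ITT, losses before 12 months as events, the same estimator and interval, and the one-sided exact test. Fix the null and the cut-off before outcomes are seen. At a 40% null this is 13 or more of 20 alive, with a level of 2.1%. Restate the power as 77%. Remove the provision to choose the Stratum C null at analysis.
- **(b) Keep it descriptive.** Report the estimate with a confidence interval, and delete the Stratum C test, power and null-rate wording from 10.2.1.

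Either route needs wording changes only, with no extra patients, visits or data. The cost is giving up a choice that could otherwise be made after the results are known. Under (a) the sponsor also has to accept a stated power slightly below 80% at the 40% null.

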10.4 Evaluation of Safety

Analyses will be performed for all patients having received at least one course of study therapy. The study will use the NCI CTCAE v5.0.

11 Data Reporting/Regulatory Requirements

11.1 Data Reporting

11.1.1 Method

The Principal Investigator and/or his/her designee will prepare and maintain adequate and accurate participant case histories with observations and data pertinent to the study. Study specific Case Report Forms (CRFs) will document safety and treatment outcomes for safety monitoring and data analysis. All study data will be entered into Advarra® via standardized CRFs in accordance with the CTMS study calendar, using single data entry with a secure access account. The Clinical Research Coordinator (CRC) will complete the CRFs as soon as possible upon completion of the study visit; the Investigator will review and approve the completed CRFs.

The information collected on CRFs shall be identical to that appearing in original source documents. Source documents will be found in the subject's medical records maintained at each PNOC site. For participating sites, source documents will be maintained per institutional guidelines. All source documentation should be kept in separate research folders for each subject.

In accordance with federal regulations, the Investigator is responsible for the accuracy and authenticity of all clinical and laboratory data entered onto CRFs. The PI will approve all completed CRFs to attest that the information contained on the CRFs is true and accurate.

All source documentation and CTMS data will be available for review/monitoring by the UCSF DSMC and regulatory agencies.

The Principal Investigator will be responsible for ensuring the accurate capture of study data. At study completion, when the CRFs have been declared to be complete and accurate, the database will be locked. Any changes to the data entered into the CRFs after that time can only be made by joint written agreement among the Study Chair, the Trial Statistician, and the PNOC Project Leader.

Responsibility for Data Submission

Please refer to Appendix C for data submission timelines.

11.2 PNOC Oversight and Monitoring Plan

This is a multicenter trial. The UCSF Helen Diller Family Comprehensive Cancer Center Data Safety Monitoring Committee (DSMC) will be the main monitoring entity for this study. The UCSF DSMC will work together with participating member institution PIs and DSMCs to monitor each subject on study. The DSMC will routinely review all adverse events and suspected adverse reactions considered "serious". The UCSF DSMC will audit study-related activities to ensure that the study is conducted in accordance with the protocol, local standard operating procedures, FDA regulations, and Good Clinical Practice (GCP). Significant results of the DSMC audit will be communicated to the IRB and the appropriate regulatory authorities at the time of continuing review, or in an expedited fashion, as applicable. Please see Appendix D PNOC Data Safety and Monitoring Plan for more information.

11.3 Multicenter Communication

The PNOC operations office provides administration, data management, and organizational support for the participating sites in the conduct of the clinical trial. The PNOC Operations Office will coordinate, at minimum, quarterly conference calls with the PNOC member institutions to discuss risk assessment. The following items will be discussed, as appropriate:

- Enrollment information
- Adverse events (i.e. new adverse events and updates on unresolved adverse events and new safety information)
- Protocol violations
- Other issues affecting the conduct of the study

11.4 Record Keeping and Record Retention

The Principal Investigator for each PNOC institution is required to maintain adequate records of the disposition of the drug, including dates, quantity, and use by subjects, as well as written records of the disposition of the drug when the study ends per institutional guidelines.

The site Principal Investigator is required to prepare and maintain adequate and accurate case histories that record all observations and other data pertinent to the investigation on each individual administered the investigational drug or employed as a control in the investigation. Case histories include the case report forms and supporting data including, for example, signed and dated consent forms and medical records including, for example, progress notes of the physician, the individual's hospital chart(s), and the nurses' notes. The case history for each individual shall document that informed consent was obtained prior to participation in the study.

Study documentation includes all CRFs, data correction forms or queries, source documents, Sponsor-Investigator correspondence, monitoring logs/letters, and regulatory documents (e.g., protocol and amendments, IRB correspondence and approval, signed subject consent forms).

Source documents include all recordings of observations or notations of clinical activities and all reports and records necessary for the evaluation and reconstruction of the clinical research study.

In accordance with FDA regulations, the investigator shall retain records for a period of 2 years following the date a marketing application is approved for the drug for the indication for which it is being investigated; or, if no application is to be filed or if the application is not approved for such indication, until 2 years after the investigation is discontinued and FDA is notified.

11.5 Coordinating Center Documentation of Distribution

It is the responsibility of the PNOC operations office to maintain adequate files documenting the distribution of study documents as well as their receipt (when possible). The HDFCCC recommends that the PNOC operations office maintain a correspondence file and log for each segment of distribution (e.g., FDA, drug manufacturer, participating sites, etc.).

Correspondence file: should contain copies (paper or electronic) of all protocol versions, cover letters, amendment outlines (summary of changes), etc., along with distribution documentation and (when available) documentation of receipt.

Correspondence log: should be a brief list of all documents distributed including the date sent, recipient(s), and (if available) a tracking number and date received.

At a minimum, the PNOC operations office must keep documentation of when and to whom the protocol, its updates and safety information are distributed.

